1. PROTOCOL SYNOPSIS

Table 1

Protocol Title	A two comparator, controlled phase 3 study of OM3 Tear formulation versus OPTIVE ADVANCED Unit Dose and OPTIVE Unit Dose eye drops in patients with and without evaporative dry eye.
Background	
 ○ The normal tear film is a relatively stable, thin film composed of a superficial lipid layer and an aqueous layer intermixed with a mucous gel layer, which is partially adherent to the corneal and conjunctival surface epithelium ○ Dysfunction of one or more components of the tear film can lead to loss of tear film stability and symptoms of dry eye ○ The majority of patients with dry eye are prescribed artificial tears to alleviate symptoms and maintain a healthy ocular surface ○ OM3 Tear is a new unit dose emulsion, containing flaxseed/castor oil, which is being developed by [REDACTED]. It is desirable to understand the effect that this new emulsion has on tear film evaporation and tear lipid profile via interferometry, in patients with evaporative dry eye (EDE) and those without (non-EDE). It would also be valuable to evaluate the retention time of the lipid components of the new emulsion via tear collection and analysis in EDE and non-EDE patients
Study Design	Single centre, double-masked, randomized, 3 arm comparison of OM3 Tear eye drops to two comparators.
Aims and Objectives	To measure tear film evaporation rate, tear lipid profile via interferometry and tear lipid components before and 15 mins, 1 hour and 4 hours after the first dose, and again after 4 weeks of use of the emulsion OM3 Tear eye drops, compared to two comparators (Optive Advanced Unit Dose and Optive Unit Dose).
Recruitment	September 2016
Study Start & End Dates	September 2016 – April 2017
Sample size	
Up to 40 participants will be recruited (approx. 20 EDE and 20 non-EDE subjects). This sample size was calculated on the basis of detecting a difference in:
 
 ○ tear evaporation rate between the eye drops of 36 gm⁻²/h where the expected standard deviation of the measurement is 50 gm⁻²/h, assuming an estimate of type 1 error $\alpha = 0.05$ and power of 80% for a two tailed test¹
Subject Source	UNSW and general community


Selection criteria
	
General Inclusion Criteria
 
 ○ Able to read and comprehend English and give informed consent as demonstrated by signing a record of informed consent; ○ Over 18 years of age; ○ Not wearing contact lenses in the past 3 months before enrolling ○ Willing to use eye drops and comply with the study visit schedule as directed by the Investigator; ○ Habitual (corrected or uncorrected) visual acuity of 6/9.5 or better in each eye; ○ At the Screening visit (Day -14), patients must have Ocular Surface Disease Index (OSDI) score >18 (0 to 100 scale). At Baseline (Day 1) visits, patients must have OSDI score > 12 to continue in the study. ○ TBUT≤10sec in at least 1 eye at Screening visit and Baseline visit ○ Corneal sodium fluorescein staining score ≥ 1 and <4 (Oxford scheme) at Screening and Baseline visit. 
Additional Inclusion Criteria for EDE Classification
 
 ○ Tear Evaporation Rate (TER) ≥ 110 - To be confirmed (TBC) 
Additional Inclusion Criteria for non-EDE Classification
 
 ○ Tear Evaporation Rate (TER) < 110 (TBC) 
For patients who have one eye meeting EDE criteria, and other eye meeting non-EDE criteria, their Schirmer score will be used to determine the classification. If their Schirmer score is >10 in both eyes, they will be classified in the EDE group.
 
General Exclusion Criteria
 
 ○ Schirmer test (with anesthesia) ≤ 2 mm in either eye at Screening ○ Patients who are currently using topical ocular medication or have used topical ocular medication within 2 weeks of the Screening visit. Patients who are being treated bilaterally with a marketed artificial tear for dry eye can be considered, provided they discontinue use at the Screening visit; ○ Any active anterior segment disease excluding blepharitis; ○ Any systemic disease that may affect ocular health e.g. Graves disease, and auto-immune diseases such as ankylosing spondylitis, multiple sclerosis and systemic lupus erythematosus; ○ History of epilepsy or migraines exacerbated by flashing, strobe-like lights; ○ Rigid or soft contact lens wearer, including orthokeratology; ○ History of eye surgery within 6 months prior to enrolment in the study; ○ Previous corneal refractive surgery.

Visit Schedule – 3 arm study
	
Visit 1 (Day -14): Screening visit, dispensing run-in product (Refresh Plus)
 
ARM 1:
 
Visit 2a (Day 1): Pre-instillation and 15 min (± 5 min) post-instillation assessment - Eye Drop #1
 
Visit 2b (Day 1): 1 hour (± 15 min) post-instillation assessment - Eye Drop #1
 
Visit 2c* (Day 1): 4 hour (± 30 min) post-instillation assessment - Eye Drop #1
 
Visit 3 (4 weeks): 4 week assessment - Eye Drop #1
 
ARM 2: (after minimum 2 week wash-out period using run-in product Refresh Plus)

	
Visit 4a ([6 weeks): Pre-instillation and 15 min (\pm 5 min) post-instillation assessment - Eye Drop #2
 
Visit 4b (6 weeks): 1 hour (\pm 15 min) post-instillation assessment - Eye Drop #2
 
Visit 4c* (6 weeks): 4 hour (\pm 30 min) post-instillation assessment - Eye Drop #2
 
Visit 5 (10 weeks): 4 week assessment - Eye Drop #2
 
ARM 3: (after minimum 2 week wash-out period using run-in product Refresh Plus)
 
Visit 6a (12 weeks): Pre-instillation and 15 min (\pm 5 min) post-instillation assessment - Eye Drop #3
 
Visit 6b (12 weeks): 1 hour (\pm 15 min) post-instillation assessment - Eye Drop #3
 
Visit 6c* (12 weeks): 4 hour (\pm 30 min) post-instillation assessment - Eye Drop #3
 
Visit 7 (16 weeks): 4 week assessment Eye Drop #3
 
Note: Subjects are NOT to instil any eye drops within 3 hours prior to the scheduled visits
 
* 4 hour assessments will only be conducted on participants who are able to attend this additional visit on the same day as the initial assessment

Procedure
	
Standard ocular examination and non-standard ocular examination procedures will be carried out at the scheduled visits.
 
Standard optometric procedures may include:
 
 ○ Subjective questionnaires (OSDI, Likert and VAS) ○ Corneal and conjunctival staining (Fluorescein and Lissamine Green) 
Non-standard optometric procedures may include:
 
 ○ Tear evaporation rate (Modified Vapometer, Delphin Technologies) ○ Tear Break-Up Time (with fluorescein) and lipid layer grade ○ Tear film lipid layer thickness (LipiView Interferometer) ○ [REDACTED] ○ [REDACTED] ○ [REDACTED]

Study Endpoints
	
The primary endpoint is a measurable difference in tear evaporation rate between the eye drops after initial application (15 min) and/or after 1 hour and/or 4 hours of application and/or after 4 weeks of daily use.
 
The secondary endpoints are (i) a measurable difference in TBUT between the

	
eye drops after initial application (15 min) and/or after 1 hour and/or 4 hours of application and/or after 4 weeks of daily use and (ii) a measurable difference in symptom improvement between the eye drops after initial application (15 min) and after 4 weeks of daily use.

Statistical Considerations
	
Paired t-tests, repeated measures ANOVA or linear mixed model analysis using Bonferroni adjustment for multiple comparisons and p value set at $p < 0.05$. Mann Whitney U test will be used to compare tear film lipidome between the eye drops.

IRB Status & Details
	
This clinical research study requires approval from the Human Research Ethics Committee at the University of New South Wales prior to study initiation, any advertising, and participant enrolment.
 
 ○ HREC meetings held monthly ○ Lead time for new applications: approx. 2 months

Dissemination of Results
	
 ○ Publication in peer-reviewed journals ○ Presentation at International conferences

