5. STUDY OBJECTIVES AND CLINICAL HYPOTHESIS

5.1. *Study Objective*

The objective of this study is to measure tear film evaporation rate, tear lipid profile via interferometry and tear lipid components with the use of the emulsion OM3 Tear eye drops, compared to two comparators (Optive Advanced Unit Dose and Optive Unit Dose) in subjects with EDE and those without (non-EDE)

5.2. *Clinical Hypothesis*

Tear evaporation rate as measured with the Vapometer is better (i.e. lower) with the emulsion OM3 Tear formulation compared to at least one of the two comparators at one or more of the post eye drop instillation time-points.

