 # = eye drop
 a = Baseline and 15 min post-eye drop assessment
 b = 3-5 hour post-eye drop assessment
 c = 4 week post-eye drop assessment

*Visits 2b, 3b and 4b are scheduled 4 hours (± 30 mins) after the corresponding visits 2a, 3a and 4a on the same day, and therefore are not compulsory for all study participants to attend. Only those who are able to attend this visit will complete the assessment visits 2b, 3b and 4b.

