6.2. Primary Endpoint

The primary endpoint is a measurable difference in tear evaporation rate (Vapometer) between the eye drops after initial application (15 min) and/or after 1 hour and/or 4 hours of application and/or after 4 weeks of daily use.

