13.3. Accountability of Data

Individual data points that are missing will be excluded from analysis involving only those specific variables. A participant's complete visit data will not be excluded if some of the observations are missing. Data from unscheduled visits will be used only for adverse response analysis. Inclusion of outliers in the analysis will be based on the magnitude of change in test statistic with and without the outliers. Outliers will preferably be retained unless there is significant change in test results.

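### The 4-hour reading can carry the primary claim alone, yet attendance is optional, so neither a fair between-drop comparison nor the stated 80% power is assured at that time point

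*Combined protocol and SAP*

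**What the plan says.** Section 6.2 defines the primary endpoint as a difference in tear evaporation rate between the drops "after initial application (15 min) and/or after 1 hour and/or 4 hours of application and/or after 4 weeks of daily use". The synopsis and section 6 say the same. Under section 5.2 the hypothesis is met if the rate is lower with OM3 Tear "compared to at least one of the two comparators at one or more of the post eye drop instillation time-points". A 4-hour result against one comparator is therefore enough.

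The 4-hour visit is optional in both visit schedules. The synopsis states that "4 hour assessments will only be conducted on participants who are able to attend this additional visit" on the same day. The footnote to Table 4 (section 6.1.1) describes visits 2b, 3b and 4b as "not compulsory for all study participants to attend".

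On missing data, section 13.3 says: "Individual data points that are missing will be excluded from analysis involving only those specific variables". It adds that the rest of a participant's visit data is kept. Section 13.1.1 gives one sample-size calculation (difference 36, SD 50, two-sided alpha 0.05, power 80%, up to 40 participants, about 20 per stratum). It names no time point and states no allowance for absence.

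**The concern.** Order is randomised and every participant is meant to use all three drops, so the comparisons are within person. A between-drop pair at 4 hours exists only if the participant attends the 4-hour visit in both periods. The plan sets no minimum number of such pairs, does not require attendance to be consistent across periods, and does not ask for reasons for absence.

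Two things are at stake:

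- **Bias.** The visit comes after that period's drop has been instilled. If a participant attends in some periods and not others, attendance may be related to the response to the drop. Leaving out the missing readings does not correct for that.
- **Precision.** A primary claim could rest on a subset of unknown size, to which the power statement in 13.1.1 need not apply.

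Reconciling the visit labels does not remove the problem, because both schedules make the 4-hour reading optional.

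**Working it through.** **Inputs.** From 13.1.1: difference 36, SD 50, two-sided alpha 0.05, power 80%, about 20 participants per stratum, up to 40 in all. From 13.1.3: Bonferroni adjustment, with no number of comparisons given. Assumptions: 50 is the SD of the within-person difference (the plan does not say); the Bonferroni family is 2 comparators × 4 time points = 8; the 4-hour attendance rate is unknown, so a range is shown.

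**Formula.** Paired t-test with n complete pairs: power = P(|T| > t(1 − α/2, n − 1)), where T is noncentral t with n − 1 degrees of freedom and noncentrality (36/50)√n = 0.72√n.

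**The plan's own figure.** The normal approximation gives (1.960 + 0.842)²/0.72² = 15.1. The exact paired t gives 18 pairs. That is close to the 20 planned per stratum (18/0.9 = 20 if 10% dropout is assumed). Two parallel groups would need about 31 each, which does not match. The stated size is thus best reproduced as a paired test within a stratum.

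**Power by number of complete 4-hour pairs**

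| Pairs | α = 0.05 | α = 0.05/8 = 0.00625 |
|---|---|---|
| 40 | 99.3% | 94.5% |
| 28 | 95.6% | 79.1% |
| 20 | 86.3% | 56.7% |
| 18 | 82.1% | 49.5% |
| 17 | 79.6% | 45.7% |
| 14 | 70.2% | 33.8% |
| 10 | 52.9% | 18.3% |

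For 80% power, 18 complete pairs are needed at 0.05 and 29 at 0.05/8.

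- **Within a stratum of 20, at 0.05:** up to two missing pairs can be absorbed. A third takes power below 80%.
- **Strata pooled (40):** 18/40 = 45% complete pairs suffice at 0.05, and 29/40 = 73% at 0.05/8.

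**From attendance to pairs (70% attendance assumed).** If visits are attended independently, both readings exist for 0.7² = 0.49 of participants: about 10 of 20 (53% power at 0.05) or about 20 of 40 (86%). If the same people attend every time, pairs exist for 14 of 20 (70%) or 28 of 40 (96%).

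**If 50 is instead the SD of one reading,** with zero correlation between periods, the SD of the difference is 50√2 = 70.7. Then 33 complete pairs are needed at 0.05. Power is 88% with all 40 and 58% with 20.

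**Other time points.** The synopsis lists paired t-tests, repeated measures ANOVA or a linear mixed model; 13.1.3 omits the mixed model. A repeated measures ANOVA across all time points normally needs complete cases, so it could drop the 15-minute and 4-week readings of people who missed 4 hours. Tests at each visit, or a mixed model, would not.

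**The case against.** A reader might infer that the trial lacks its stated power at 4 hours. The documents do not support that. The hypothesis is not stratified, and nothing says the primary comparison is run per stratum. With the strata pooled, even independent 70% attendance leaves about 20 pairs and 86% power at 0.05. The 57% at 0.05/8 with 20 pairs arises with full attendance in a stratum, so it reflects the Bonferroni adjustment and not the optional visit. What stands is that the power is not assured.

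A reader might also infer that participants decide visit by visit, according to how their eyes feel. The text speaks only of being able to attend, and the Table 4 footnote can be read as one group completing all three visits. In that case randomised order leaves the within-person contrast fair among those who attend, and the loss is mainly generalisability and precision. Variation by period is allowed by the text, not stated in it.

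Likewise, loss of non-attenders' other readings is only a possibility. The synopsis lists a mixed model, 13.1.3 speaks of tests at each visit, and 13.3 says visit data are not excluded because some observations are missing.

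Finally, 4 hours is among the study's stated aims, so making it secondary has a real cost. That is fair. It does not explain why a reading that can decide the trial is left to availability.

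**Conclusion.** The point holds as a cheap improvement that should be made. An optional visit is one of four primary time points, it can support the claim alone, and nothing protects the comparison made there. Period-varying attendance could bias the comparison; consistent attendance mainly narrows the population and reduces precision.

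The 80% power is conditional. With 50 as the SD of the paired difference and alpha 0.05, it fails within a stratum of 20 at three or more missing pairs. It holds under pooling with at least 18 of 40 complete pairs, or 29 of 40 if Bonferroni covers an assumed eight comparisons. The attendance rate, the meaning of the SD, the size of the family and the choice between pooled and per-stratum analysis are all left open by the plan, so no single figure for the loss can be given.

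**What to change.** 1. Reconcile the visit tables. The synopsis has a 1-hour visit, whereas Tables 4 and 5 do not; they label the second visit of each period 3-5 hours, and the Table 4 footnote also puts it at 4 hours ± 30 minutes.
2. In the synopsis and sections 6 and 6.2, limit the primary time points to those every participant attends, make 4 hours secondary, and align section 5.2.
3. At enrolment, before randomisation, ask each participant to commit to the 4-hour visit in all three periods or in none. Attendance then cannot follow the response to a particular drop, so far as the commitment is kept.
4. In 13.1.3, name the linear mixed model already listed in the synopsis as the analysis of tear evaporation rate, so that partial data are kept. Report the number of complete 4-hour pairs for each comparison. The model does not remove bias if absence depends on the unseen 4-hour state, which is why step 3 matters.

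The change is to protocol wording and adds no visits. The cost is that a 4-hour effect becomes a secondary claim. A small gain is that, if 1 hour stays in, the assumed family falls from 8 to 6 tests and power at 20 pairs rises from 57% to 61%. If the sponsor wants 4 hours to remain primary, the alternative is to make the visit compulsory, or to set a minimum number of complete pairs and record reasons for absence, at the price of a heavier burden on participants or on recruitment.

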4. BACKGROUND INFORMATION

4.1. Background and Clinical Rationale

The normal tear film is a relatively stable, thin film composed of a superficial lipid layer and an aqueous layer intermixed with a mucous gel layer, which is partially adherent to the corneal and conjunctival surface epithelium. Dysfunction of one or more components of the tear film can lead to loss of tear film stability and symptoms of dry eye. The majority of patients with dry eye are prescribed artificial tears to alleviate symptoms and maintain a healthy ocular surface.

The purpose of this study is to evaluate the retention time of the lipid components of the new emulsion OM3 Tear eye drops via tear collection and analysis in evaporative dry eye (EDE) and non-EDE patients. Tear film evaporation rate, tear lipid profile via interferometry and tear lipid components will be evaluated before and 15 mins, 1 hour and 4 hours after the first dose, and again after 4 weeks of use of the emulsion OM3 Tear eye drops, compared to two comparators (Optive Advanced Unit Dose and Optive Unit Dose).

4.2. Summary

4.2.1. Risks and Benefits

Risks of the Clinical Trial

It is possible that participants may have an allergic reaction to any the study eye drops. Signs of ocular allergy (e.g. redness, itching and watering) will be treated by immediate discontinuation of use of the study eye drops and participation in the study. However, participants will be monitored until ocular signs and symptoms have returned to normal. Topical and/or oral antihistamines may be prescribed if deemed appropriate. The participant will be referred for appropriate medical treatment if required.

Any potential participants with a self-reported allergy/sensitivity to any of the study eye drops will be excluded from the study.

The Lipiview Ocular Surface Interferometer uses flashing strobe-like lights which may have an adverse effect on participants with a history of epilepsy or migraines. Any potential participants with epilepsy or a history of migraines exacerbated by flashing, strobe-like lights will be excluded from the study.

Benefits of the Clinical Trial

Participants will receive ocular lubricant treatment for their dry eye condition. However, there is no guarantee or promise that the participants will receive any health benefits from this clinical trial. The study eye drops and participants' optometric care will be provided free of charge for the duration of the clinical trial.

4.2.2. Guidelines and Regulations

The clinical trial will be conducted in accordance with the protocol, the Declaration of Helsinki (see Appendix 1), ICH GCP and local regulations as applicable including TGA and NH&MRC guidelines.

4.2.3. Trial Population

40 participants will be recruited (approx. 20 EDE and 20 non-EDE subjects).

5. STUDY OBJECTIVES AND CLINICAL HYPOTHESIS

5.1. *Study Objective*

The objective of this study is to measure tear film evaporation rate, tear lipid profile via interferometry and tear lipid components with the use of the emulsion OM3 Tear eye drops, compared to two comparators (Optive Advanced Unit Dose and Optive Unit Dose) in subjects with EDE and those without (non-EDE)

5.2. *Clinical Hypothesis*

Tear evaporation rate as measured with the Vapometer is better (i.e. lower) with the emulsion OM3 Tear formulation compared to at least one of the two comparators at one or more of the post eye drop instillation time-points.

6. STUDY DESIGN

This study is a single centre, double-masked, randomized, 3-arm comparison of emulsion OM3 eye drops compared to two comparators. All study subjects will attend a Screening visit and receive REFRESH PLUS® for 2 weeks during a run-in period prior to randomization. Subjects will be randomized as to the order of allocation to use the OM3 Tear eye drop and the two comparators. For each arm of the study, assessments will be conducted prior to eye drop instillation and 15 min, 1 hour and 4 hours post-instillation. Subjects will then be dispensed with the randomized study eye drop and instructed to instill 1 to 2 drops of their assigned study product in each eye, as needed, but at least twice daily, for 4 weeks. Subjects will attend a 4 week visit assessment and then undergo a minimum 2 week wash-out period using run-in product REFRESH PLUS® before returning to complete the next arm of the study. These procedures will be repeated until the subjects have completed all 3 arms of the study.

The primary endpoint is a measurable difference in tear evaporation rate between the eye drops after initial application (15 min) and/or after 1 hour and/or 4 hours of application and/or after 4 weeks of daily use.

All proposed procedures conform to the NHMRC Statement on Human Experimentation.

Participants are considered enrolled when they have signed the informed consent form and are regarded as part of the clinical trial population.

6.1. Methodology / Study Visits

6.1.1. Data Requirements per Visit with Visit window (\pm days)

The data requirements for each visit are shown in Table 4.

Table 4

	Visit 1	Visit 2a	Visit 2b*	Visit 2c	Visit 3a	Visit 3b*	Visit 3c	Visit 4a	Visit 4b*	Visit 4c
Timeline	Day - 14	Day 1 #1	Day 1 #1	4 weeks #1	6 weeks #2	6 weeks #2	10 weeks #2	12 weeks #3	12 weeks #3	16 weeks #3
Procedure										
Informed Consent	Y	N	N	N	N	N	N	N	N	N
Inclusion/Exclusion criteria	Y	Y	N	N	N	N	N	N	N	N
Ocular, medical history, medications, demographics	Y	N	N	N	N	N	N	N	N	N
Updated history, symptoms, problems	Y	Y	N	Y	Y	Y	Y	Y	Y	Y
Vision tests	Y	Y	Y	Y	Y	Y	Y	Y	Y	Y
Biomicroscopy (ocular health, staining)	Y	Y	N	Y	Y	N	Y	Y	N	Y
Meibomian gland assessment	Y	N	N	N	N	N	N	N	N	N
Schirmer test (eligibility)	Y	N	N	N	N	N	N	N	N	N
Instill eye drops	Y	Y	N	N	Y	N	N	Y	N	N
Tear evaporation rate	N	Y	Y	Y	Y	Y	Y	Y	Y	Y
Eye photo (ocular surface area)	Y	N	N	N	N	N	N	N	N	N
Schirmer test (tear collection)	N	Y	Y	Y	Y	Y	Y	Y	Y	Y
LipiView	N	Y	Y	Y	Y	Y	Y	Y	Y	Y
TBUT (fluorescein)	N	Y	Y	Y	Y	Y	Y	Y	Y	Y
Questionnaires (OSDI, VAS)	Y	Y	Y	Y	Y	Y	Y	Y	Y	Y

Y = Yes, required information, N = No, not required
